Appendix C (The IRB-approved Protocol)

Primary objectives:

- 1) Identify and characterize factors affecting children's exposures to chemical ingredients from consumer products found in their everyday environment in order to support the data and modeling needs of the exposure components of EPA's national research programs;
- 2) Evaluate the pilot study data metrics for incorporation in and enhancement of CDC's ability to understand the relationship between environmental exposures and asthma in green versus traditional low-income housing;
- 3) Compare multimedia measurements and survey data between pre- and post-renovation time points in green and traditional low-income housing to assess exposure related changes in the residence and participants due to renovation activities.

Objective 1 will examine how influential personal, housing, and community factors are in determining children's exposures. Results will be used to directly compare siblings and determine how personal and housing factors vary. For siblings living in the same household, we hypothesize that shared exposures to housing and community factors both before and after building renovation will be similar. Thus, we hypothesize that personal exposure factors, including activities and behaviors, will most influence exposure to chemical and biological agents found in their indoor environment. Furthermore, the variability in personal exposure factors will be a function of age, lifestage, and health status (asthma versus no asthma). We can use this information to parameterize, refine, and evaluate exposure and dose models for consumer product active ingredients. Because of the lack of data on personal, housing, and community factors from the same cohort, it is necessary to collect these data to evaluate this objective.

Objective 2 will evaluate the pilot study methods and approaches for measuring exposures to consumer product chemicals and identifying exposure factors. It will also establish suitability for incorporation in future Green Housing Study sites and for future research directions. Our data collection effort is intended to complement the multimedia measurements and information being collected by CDC in the Green Housing Study. Methods found to be suitable in the pilot study will allow EPA and CDC to improve the evaluation of relationships between environmental exposures and asthma in the renovated and non-renovated homes.

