3.2 Study Location

The third study site will be determined by CDC based on site selection criteria detailed in their funding opportunity announcement. In the Green Housing Study third study site, the target sample size is 32 green renovated homes and 32 comparison homes. The target sample size for the EPA pilot study add-on is the same number of families as are recruited to participate in the Green Housing Study. Thus, n=64 younger siblings (only one sibling per household) will be the maximum number that could be enrolled as part of the EPA pilot study add-on. Participants in each family will include the index child and a sibling of the index child living in the same household, as well as the mother/caregiver. The index child is defined as the child recruited to participate in the Green Housing Study who ranges in age from 7-12 years with a doctor diagnosis of asthma. By including both the index child and a sibling, it is an opportunity to collect exposure information for two children living in the same household, allowing us to explore differences in exposure based on lifestage.

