3.3 Sampling the Participants

3.3.1 Sample Selection and Eligibility

Eligibility for the EPA pilot study add-on will be limited to families who enroll to participate in the Green Housing Study. In addition to the index child, a sibling of the index child residing in the same home will be enrolled. The sibling age range of most interest is 0 – 3 years. However, since it may not be possible to recruit siblings in that age range from every family, eligibility will be based on the availability of the youngest sibling in the 0 to 12 year age range. An asthma

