Appendix C (The IRB-approved Protocol)

house dust loading measurements or personal samples in order to model children's soil and dust ingestion rates (objective 10). Finally, the interaction of time spent in different locations with housing and community factors such as crime rate, transportation options, and perception of children's safety will be quantified.

From the activity survey results, descriptive statistics of reported time spent in microenvironments and activities will be calculated. In addition, GPS-based time spent in microenvironments will be calculated using EPA's MicroTrac model (Breen et al., 2014). This model takes as input a GPS time-series and a general location of the participant's home and using a computational algorithm calculates time spent at home and in travel (in vehicles). The MicroTrac results will be compared with the survey results as in Breen et al. (2014). Differences among age groups, genders, and asthmatic/non-asthmatic children for both survey and GPS results will be quantified and tested using appropriate parametric or non-parametric techniques.

Children's activities are an important determinant of the types and amounts of chemicals encountered (McCurdy, 2000). Therefore, time spent in exposure-relevant activities (e.g., time spent with pet or exercising) will be characterized via standard methods (Xue et al., 2004). A primary analysis will evaluate age- and asthma-dependent differences in activity level in children living in the same household. The results from this analysis will aid in characterizing/elucidating the contributions of age, health, socioeconomic status, and other factors to describe the variability in activity levels. Similar to location, the interaction between housing and community factors (e.g., crime or noise pollution) and exposure relevant activities will be addressed. In addition, the location of high-dose rate activities (e.g., exercise) for these children will be compared to other, previously studied child cohorts to assess the influence of community or socioeconomic status-driven factors (such as distance from pollutant sources, or indoor versus outdoor exercise locations).

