Appendix C (The IRB-approved Protocol)

Objective 9: Use settled dust to identify and classify indoor fungal populations and functions overrepresented among fungal biota

One non-chemical stressor found in a home is mold. Molds are potential stressors because they produce allergens which have been shown to cause and or exacerbate allergies, diseases such as asthma, and affect immune system function. Because there are so many allergens, we measure the populations of molds as indicators of these agents.

We will use both the EDC method and the Swiffer settled dust collection protocol to evaluate the renovation process because both approaches provide insights into different timeframes and conditions for exposure. The EDC method is a measure of the mold cells in the air at a given time and the collection of settled dust is limited to short exposure time points. Additionally, the Swiffer settled dust collection protocol may represent what a child has been exposed to for a longer time period (many weeks to months depending on the frequency of house cleaning). Each method provides a different insight into the mold exposures in the home which is why both methods will be used and the results analyzed and compared.

DNA analysis of the dust collected using the Swiffer settled dust collection protocol will use quantitative PCR (polymerase chain reaction; qPCR). DNA analysis of the dust collected using the EDC method will be analyzed using high-throughput sequencing technology. Both approaches will be used to identify and classify indoor fungal populations and functions overrepresented among fungal biota.

Fungal DNA will be extracted from the EDC dust samples and analyzed using HTS analysis. This analysis will provide a holistic identification of the diverse indoor fungal population both pre/post renovation. This fungal DNA HTS analysis will provide an exposure metric for understanding which fungal populations are associated with asthma in children. In addition, the metagenomic data generated from the DNA of dust samples will be used to identify genes and functions that are overrepresented among the fungal biota. The pre/post renovation analysis will provide an exposure metric to understand the possible association, if any, between airborne mold and asthma in children.

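### The recruitment rule ties asthma to age, so the planned asthma contrasts, run as written, would carry much of any age effect; an age-adjusted asthma estimate is possible but imprecise

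*Protocol*

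**What the plan says.** **Who is enrolled.** Section 3.2 defines the index child as one who "ranges in age from 7-12 years with a doctor diagnosis of asthma". Section 3.3.2 confines add-on recruitment to families already in the main study, so every home contains such a child. The inclusion criteria in Table 2 of Appendix A also require asthma-related symptoms in the past six months.

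For the second child, section 3.3.1 states: "The sibling age range of most interest is 0 – 3 years". Section 3.3.2 sets the order of preference as 0-3, then 4-6, then 7-12 years, and takes the youngest sibling who will participate. There is one sibling per home and at most 64 in all; fewer are expected. Section 3.3.1 leaves sibling asthma open: it is neither a requirement nor a bar. Item 1 of the questionnaire asks about a doctor's diagnosis for each child.

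**What is to be compared.**
- Section 5.0, Objective 8: "A primary analysis will evaluate age- and asthma-dependent differences in activity level in children living in the same household".
- The same section: "Differences among age groups, genders, and asthmatic/non-asthmatic children for both survey and GPS results will be quantified and tested".
- Section 2.2, under Objective 1: "the variability in personal exposure factors will be a function of age, lifestage, and health status (asthma versus no asthma").
- Section 5.0, Objective 9: "This fungal DNA HTS analysis will provide an exposure metric for understanding which fungal populations are associated with asthma in children".

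Section 5.0 lists t-tests or F-tests by sibling and age group for Objective 1, and a regression on product, activity, location and housing variables. Neither age nor asthma is named as a covariate in that regression. Section 2.4 names sample size as the main limitation and does not mention confounding of asthma with age.

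**The concern.** The design determines which children have asthma and, largely, how old they are. All index children have asthma and are of school age. A child without asthma can only be a sibling, and siblings are sought as young as possible. A within-home index-minus-sibling difference is therefore mostly an age difference with an asthma difference added to it. A pooled asthmatic versus non-asthmatic test compares groups that lie years apart in age.

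This matters most for the outcomes in question. Activity, time in locations and contact with household media can be expected to differ between a toddler and a ten-year-old whether or not either has asthma. Section 5.0 intends the Objective 8 results to help apportion variability between age, health and other factors, and contrasts that mix age and asthma cannot do that.

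For Objective 9, dust is measured per home and every home contains a child with asthma. The study therefore has no asthma-free home against which to show that a fungal population goes with having asthma.

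**Working it through.** **The plan's own figures.** The protocol states no sample size or power for any asthma contrast, so there is nothing to reproduce. The one add-on power example (limonene, section 2.3) compares renovated with non-renovated homes and does not bear on this point.

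**Inputs.** From the protocol: index age 7-12 with asthma always present; sibling age bands 0-3, 4-6 and 7-12; at most 64 pairs. Assumed, because the protocol does not give them: ages uniform over whole years within each band, the sibling age mix, and sibling asthma of 0%, 9.1% or 30% unrelated to age. The 9.1% is the national childhood average quoted in Appendix A, B.1, used here only as the low end of the non-zero range. One value per child; two-sided alpha 0.05; power 80%, so z = 1.96 + 0.84 = 2.80. Effects are in SDs of the within-pair difference.

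**Step 1, extreme case: all siblings 0-3, none with asthma.** Mean ages are 9.5 and 1.5, and the variances are 35/12 = 2.92 and 15/12 = 1.25.
- Correlation of age with asthma: √[16 / (16 + (2.92 + 1.25)/2)] = √(16/18.08) = 0.94.
- Variance inflation for asthma in a within-pair model with a linear age difference: (8² + 4.17)/4.17 = 16.4 (simulation: 16.25).
- With the protocol's age bands, every pair has the same age-band difference and the same asthma difference. The two effects are fully aliased.

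**Step 2, all siblings 0-3, 9.1% with asthma.** 0.091 × 64 = 5.8, about 6 siblings. With age bands, the asthma effect is the index-minus-sibling difference in the 58 pairs whose sibling has no asthma, minus that in the 6 pairs whose sibling has it.
- Detectable effect: 2.80 × √(1/6 + 1/58) = 1.20 SD.
- Ignoring age: 2.80/√58 = 0.37 SD, but this estimates age plus asthma.

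**Step 3, age gap in an unadjusted comparison.** With sibling mean age S and sibling prevalence p, asthmatic minus non-asthmatic mean age is (9.5 − S)/(1 + p). For a 70/20/10 mix, S = 0.7×1.5 + 0.2×5 + 0.1×9.5 = 3.0. The gap is 6.5/1.091 = 6.0 years at 9.1% and 6.5/1.3 = 5.0 years at 30%. For equal thirds, S = 5.33 and the gaps are 3.8 and 3.2 years.

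**Step 4, range (64 pairs; correlations, inflation and detectable effects by simulation).**

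| Siblings 0-3 / 4-6 / 7-12 | Sibling asthma | Correlation | Age gap (years) | Inflation, linear age | Detectable, age bands (SD) |
|---|---|---|---|---|---|
| 100/0/0% | 0% | 0.94 | 8.0 | 16 | not estimable |
| 100/0/0% | 9.1% | 0.86 | 7.3 | 6.9 | 1.20 |
| 70/20/10% | 9.1% | 0.74 | 6.0 | 3.6 | 0.87 |
| 70/20/10% | 30% | 0.59 | 5.0 | 2.3 | 0.70 |
| equal thirds | 9.1% | 0.55 | 3.8 | 1.9 | 0.59 |
| equal thirds | 30% | 0.45 | 3.2 | 1.6 | 0.59 |

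Ignoring age gives 0.37 SD at 9.1% and 0.42 SD at 30%. With 35 pairs (illustrative), the second row becomes about 1.7 SD and the 70/20/10 rows about 1.2 and 0.95 SD. Under 70/20/10 the simulation gives only about 5-6 children aged 7-12 without asthma; under equal thirds, 15-19.

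**The case against.** The strongest reply is that the protocol does not rule out an asthma estimate. Sibling asthma is unrestricted and recorded, and siblings may be up to 12. Asthmatic and non-asthmatic siblings of similar age can be compared across homes, and homes where both children have asthma isolate the age effect. All of this stands. A reader might infer that asthma never varies between homes, or that the asthma questions cannot be answered. The documents do not support either reading. What is constant is the index child's status, and full aliasing arises only if no sibling has asthma and none is aged 7-12.

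A second reply is that Objective 8 is secondary, Objective 1 states only a hypothesis, and covariate adjustment is usual content for a statistical analysis plan. The exact model can indeed be left there. But this protocol itself fixes both the recruitment order and the contrasts, including one that it calls a primary analysis, and the two conflict without comment.

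A third reply is that Objective 9 already relates FEV1% to the mold index and mold to asthma-like symptoms. These outcomes vary among children with asthma, so those analyses are not blocked. What remains is the wording of one claim.

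It is also tempting to say that asthma status at 0-3 is largely unsettled, because a cohort cited in section 1.3 diagnosed asthma at age seven. That describes the cited study's design and does not establish the point for these siblings.

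**Conclusion.** The concern holds as strong confounding and imprecision. By recruitment rule, asthma goes with older age, and no home is free of a child with asthma. The unadjusted asthmatic/non-asthmatic tests and the within-household asthma comparison would carry much of any age effect. Across the assumed scenarios in which some siblings have asthma, the unadjusted groups lie about 3 to 7 years apart in mean age. Adjustment with age bands raises the detectable effect from about 0.4 SD to between about 0.6 and 1.2 SD with 64 pairs, and higher with fewer.

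These sizes rest on an assumed sibling age mix and asthma prevalence. No count of informative children can be read from the protocol as a bound. The direction of the problem rests only on the recruitment rule and the planned contrasts, both of which are stated.

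**What to change.** 1. **Objectives 1 and 8.** Replace the unadjusted asthmatic/non-asthmatic comparison with a model on all children that includes both age and asthma status and a household effect. It should draw on asthmatic and non-asthmatic siblings of similar age across homes, as well as on index children against siblings aged 7-12. Keep age in the model within the 7-12 band, because a sibling there may still be younger than the index child. Do not restrict the analysis to that band: doing so discards the younger siblings with asthma, who carry much of the information.
2. **Labels.** Call the raw index-minus-sibling difference a combined age-plus-asthma contrast. Report the age-adjusted asthma effect as exploratory, with its confidence interval and the numbers of siblings by age band and asthma status.
3. **Objective 9.** Reword the sentence on fungal populations to refer to association with asthma morbidity (FEV1, symptoms) among index children with asthma, in line with the analyses already planned there.
4. **Section 2.4.** Add the confounding, and the absence of asthma-free homes, as limitations.

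Cost: wording and a model statement, with no new data or visits. The price is that the asthma estimate will be openly imprecise and may be uninformative if few siblings have asthma or are aged 7-12.

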Appendix C (The IRB-approved Protocol)

Objective 9: Use settled dust to identify and classify indoor fungal populations and functions overrepresented among fungal biota

One non-chemical stressor found in a home is mold. Molds are potential stressors because they produce allergens which have been shown to cause and or exacerbate allergies, diseases such as asthma, and affect immune system function. Because there are so many allergens, we measure the populations of molds as indicators of these agents.

We will use both the EDC method and the Swiffer settled dust collection protocol to evaluate the renovation process because both approaches provide insights into different timeframes and conditions for exposure. The EDC method is a measure of the mold cells in the air at a given time and the collection of settled dust is limited to short exposure time points. Additionally, the Swiffer settled dust collection protocol may represent what a child has been exposed to for a longer time period (many weeks to months depending on the frequency of house cleaning). Each method provides a different insight into the mold exposures in the home which is why both methods will be used and the results analyzed and compared.

DNA analysis of the dust collected using the Swiffer settled dust collection protocol will use quantitative PCR (polymerase chain reaction; qPCR). DNA analysis of the dust collected using the EDC method will be analyzed using high-throughput sequencing technology. Both approaches will be used to identify and classify indoor fungal populations and functions overrepresented among fungal biota.

Fungal DNA will be extracted from the EDC dust samples and analyzed using HTS analysis. This analysis will provide a holistic identification of the diverse indoor fungal population both pre/post renovation. This fungal DNA HTS analysis will provide an exposure metric for understanding which fungal populations are associated with asthma in children. In addition, the metagenomic data generated from the DNA of dust samples will be used to identify genes and functions that are overrepresented among the fungal biota. The pre/post renovation analysis will provide an exposure metric to understand the possible association, if any, between airborne mold and asthma in children.

The ERMI values from the renovated homes will be compared to the traditional homes at each time point using regression analysis. Comparisons between the settled dust and EDC dust will be conducted both pre/post renovation and green versus traditional housing using Pearson correlations. For each child, respiratory data (FEV1%) will be evaluated in relationship to the ERMI value in the home using Pearson correlation analysis. Univariate and multivariate regression analyses will be used to explore different stressors as well as the interactions between different stressors.

Mold information will also be incorporated into statistical analyses to explore relationships between ERMI values in the homes at different times with asthma-like symptoms. The differences in concentrations in the dust samples of individual mold species at each time point will be evaluated using the Wilcoxon rank sum test. Corrections for multiple comparisons will be made using the Holms-Bonferroni test. This test will allow us to determine which mold species are significantly reduced by the renovations. Other analyses will compare the type of

